### **Secondary Endpoint Analysis**

This secondary endpoint is exploratory and does not have pre-specified performance criteria. Data will be summarized for both the ITT and PP analysis populations.

### **Analysis of Demographic and Baseline Data**

Subject demographic and baseline data will be summarized for the PP analysis population. Continuous variables will be summarized using descriptive statistics (number of subjects, mean, standard deviation, median, minimum and maximum), and categorical variables will be summarized using the count and percentage of subjects in each category.

### **Safety Analysis**

Safety will be analyzed based on the ITT analysis population. The assessment of safety will be based on the summaries of AEs, vital signs, physical examination findings, and ECGs. The Medical Monitor's assessment of seriousness and relatedness, rather than the investigator's assessment, will be used for summarizing and analyzing safety data.

Separate summaries of AEs related to use of the Test System and by severity will be prepared. The number of deaths and UADEs will also be presented, and events leading to discontinuation from the study will be listed and tabulated.

Continuous variables will be summarized by descriptive statistics, and categorical variables will be summarized using the count and percentage of subjects in each category.

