### **Medical Monitor**

The Medical Monitor (an independent physician not participating as a clinical investigator in the clinical study) will review and assess in conjunction with the Sponsor all AEs considered by the investigator to be at least possibly related to the use of the Test System to determine if they are reportable to the FDA as Unanticipated Adverse Device Effects (UADEs) per the definition in Section 10. The Medical Monitor will also review all Serious Adverse Events considered by the investigator to be at least possibly related to the use of the Test System to verify relatedness and the Serious classification.

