## 10 ADVERSE EVENT REPORTING

Adverse events (AEs) as defined below will be monitored during the study procedure. AEs may be reported by the subject, discovered by Investigator questioning, or detected through physical examination or other means at the study visit. All AEs must be recorded on the CRF. The following information about each AE will be collected: description, severity, onset and resolution dates, seriousness, relationship to the Test System, action taken, and outcome.

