### Definitions

For the purposes of this study, an **AE** is defined as any untoward medical occurrence in a subject during the study that in the opinion of the investigator is at least possibly-related to use of the Test System during the EP procedures specified in Section 9.

A serious adverse event (**SAE**) is defined as any adverse event that:

- Leads to death
- Leads to serious deterioration in the health of a subject that:
  - Results in a life-threatening illness or injury, or
  - Results in a permanent impairment of a body structure or a body function, or
  - Requires in inpatient or prolonged hospitalization  $\geq$  24 hours, or
  - Results in medical or surgical intervention to prevent life-threatening illness or injury or permanent impairment to a body structure or function, or
- Leads to fetal distress, fetal death or a congenital anomaly or birth defect

**Adverse Device Effect (ADE)** is an adverse event related to the use of an investigational medical device (the Test System).

**Anticipated Adverse Device Effects (AADEs)** are those events related to the use of the Test System that are reasonably expected to occur as a result of the subject's participation in the study. The following are AADEs based on complications reported associated with defibrillation threshold testing (Wilkoff BL), complications associated with ICD pulse generator replacement (Poole JE), and the Test System engineering hazard analysis:

- Acute kidney injury
- Acute liver injury
- Blisters
- Burn
- Cardiac arrest
- Cardiac Perforation
- Cellulitis
- Central nervous system injury
- Death
- Deep vein thrombosis
- Depression of contractile function leading to worsening of heart failure
- Heart failure needing intravenous treatment with inotropes or diuretics
- Hematoma at catheter site requiring evacuation or long-term treatment with antiplatelet or anticoagulation medication
- Hemodynamic instability
- Hemothorax
- Hospital readmission
- Infection
- Itching under Test System defibrillation or ECG electrodes
- Lead dislodgment or malfunction (requiring re-operation)
- Myocardial Injury
- Pain persistent > 7 days
- Peripheral arterial embolus
- Persistent hypotension
- Pleural effusion
- Pneumothorax
- Prolonged hospitalization
- Pulseless electrical activity (PEA)
- Recurrent VT
- Refractory VF
- Respiratory arrest/depression
- Skin Rash
- Stroke or transient ischemic attack (TIA)
- Tamponade
- Thromboembolic events

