An **Unanticipated Adverse Device Effect (UADE)** is any serious adverse effect on health or safety or any life-threatening problem or death caused by, or associated with the study device (the Test System), if that effect, problem, or death was not previously identified in nature, severity, or degree of incidence in this protocol; or any other unanticipated serious problem associated with the device that relates to the rights, safety, or welfare of subjects.

All AEs will be assessed by the investigator And the Medical Monitor according to:

- Whether the event is serious (SAE);
- The severity of the event (mild, moderate, severe);

- Mild: Awareness of signs and symptoms, but easily tolerated; are of minor irritant type, causing no loss of time from normal activities; symptoms would not require medication or a medical evaluation; signs and symptoms are transient.
- Moderate: Discomfort severe enough to cause interference with usual activities; requiring treatment, but not extended hospitalization or intensive care for the subject.
- Severe: Incapacitating with inability to do work or usual activities; signs and symptoms may be systemic in nature or require medical evaluation and/or treatment; requiring additional hospitalization or intensive care (prolonged hospitalization).
- The relationship of the event to use of the Test System:
  - Possibly Related: There is a reasonable possibility that the AE may have been primarily caused by device use. The AE has a reasonable temporal relationship to the use of the device and follows a known or expected response pattern to device, but alternative etiology is equally or more likely compared to the potential relationship to the use of the device.
  - Probably Related: There is a reasonable probability that the AE may have been primarily caused by device use. The AE has a reasonable temporal relationship to the use of the device and follows a known or expected response pattern to device. Note: this definition assumes no alternative etiology is equally or more likely compared to the potential relationship to the use of the device.
  - Definitely Related: The AE has a strong causal relationship to device use. The AE follows a strong temporal relationship to the use of the device, follows a known response pattern to the device, and cannot be reasonably explained by known characteristics of the subject's clinical state, other therapies, or change in clinical status during the electrophysiologic procedure.

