Whenever possible, the Investigator should group signs or symptoms that constitute a single diagnosis under a single AE term (e.g. redness and swelling can be combined under skin irritation).

Baseline conditions are not considered adverse events unless the condition worsens because of Test System use.

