## **Adverse Event Reporting Procedures**

SAEs deemed at least possibly related to the use of the Test System will be reviewed by the investigator and will be recorded on the CRF.

Upon awareness of a SAE, the study site must enter the data into the CRF within 3 working days. If the eCRF is not accessible the Sponsor or Sponsor representative must be notified of any SAE via [contact]).

UADEs must be reported by the investigator to the approving IRB as soon as possible, but not later than 10 working days after the investigator first learns of the effect.

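### The Medical Monitor's relatedness rating governs the safety analysis, but the Monitor has no route to rate an event the investigator did not attribute to the Test System

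*Combined protocol and SAP*

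**What the plan says.** The safety objective and endpoint (Section 3; Section 7, Study Objectives and Endpoints) are a summary of adverse events at least possibly related to the Test System, with classification of unanticipated adverse device effects (UADEs). Section 7, Safety Analysis, settles whose judgement counts: "The Medical Monitor's assessment of seriousness and relatedness, rather than the investigator's assessment, will be used for summarizing and analyzing safety data".

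Four other places decide which events reach that judgement:

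- Section 10, Definitions: an adverse event is an untoward occurrence "that in the opinion of the investigator is at least possibly-related to use of the Test System". A worsening of an existing condition is treated the same way: "Baseline conditions are not considered adverse events unless the condition worsens because of Test System use".
- Section 10, opening paragraph: "All AEs must be recorded on the CRF". This covers adverse events as just defined.
- Section 10, Adverse Event Reporting Procedures: "SAEs deemed at least possibly related to the use of the Test System will be reviewed by the investigator" and entered on the CRF.
- Section 6, Medical Monitor: the Monitor reviews "all AEs considered by the investigator to be at least possibly related to the use of the Test System" to decide whether they are reportable as UADEs, and reviews serious events under the same condition "to verify relatedness and the Serious classification".

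Section 10 also states: "All AEs will be assessed by the investigator And the Medical Monitor according to" seriousness, severity and relationship. The relationship scale has three grades: possibly, probably and definitely related.

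**The concern.** Putting an independent physician's rating ahead of the investigator's is meant to make the relatedness judgement independent of the person directing the shock. That works only if the independent rater sees the events on which the two might disagree. Here the investigator's attribution is the entry condition for being an adverse event at all, so the Monitor sees only events on which the investigator has already said yes.

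Attribution is not always easy in this setting. Subjects are undergoing electrophysiology studies, ICD replacement or VT ablation, and the list of anticipated device effects draws partly on complications of defibrillation testing and generator replacement. Device and background causes overlap. At stake is how the only safety endpoint can be read: a short or empty table of related events could mean that none occurred or that none was attributed, and the independent review cannot tell the two apart.

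**Working it through.** No figure in the plan is at issue, so there is nothing to reproduce. The check traces an event through the rules.

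**Step 1: the four possible cases.** Take any untoward event during the procedure and cross the investigator's view with the view the Monitor would form if shown it.

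- *Investigator yes, Monitor yes.* An adverse event; recorded, sent to the Monitor, counted.
- *Investigator yes, Monitor no.* An adverse event; recorded and sent to the Monitor. See step 3.
- *Investigator no, Monitor would say yes.* Not an adverse event under Section 10, Definitions. It need not be recorded as one, lies outside the events that Section 10 asks the Monitor to assess, and is outside the Section 6 referral. It is not counted.
- *Investigator no, Monitor would say no.* Not recorded and rightly not counted.

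**Step 2: the bound.** Let A be the set of events the investigator attributes and M the set the Monitor would rate at least possibly related. The analysed set is the overlap of A and M, so its count is at most the count of A. Events in M but not in A are lost. The documents give no estimate of how many there might be.

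**Step 3: the other direction.** Safety Analysis uses the Monitor's rating, and the endpoint counts events at least possibly related. Together these imply that an event the Monitor rejects leaves the related-event summary. But the scale starts at *Possibly Related*, so there is no grade in which to record the rejection, and nothing says whether the event is then listed elsewhere.

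**Step 4: two places that do not agree.** Section 6 gives the Monitor verification of relatedness for serious events only, and a UADE-reportability review for other events. Section 10 has the Monitor rate the relationship of all adverse events. In addition, Section 10 collects relationship for each adverse event, and Safety Analysis promises a separate summary of related ones. Both suggest a wider set from which related events are picked, whereas by definition every adverse event is already related in the investigator's view.

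**Step 5: other routes to the Monitor.** Section 9 collects ECG records and a physician procedure report. Section 11 (Study Data and Conduct Monitoring) has the study monitor compare CRFs with source documents. Either might bring an unattributed event to light, but neither section refers such an event to the Medical Monitor, and the definition would still require the investigator's opinion. The accurate statement is that no route is provided.

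**The case against.** The strongest reply is that this is a declared choice. The objective is limited to device-related events, in subjects already having invasive procedures, with participation confined to the procedure. The threshold is low: an event can be *Possibly Related* even when another cause is as likely or more so. This stands, and it limits how many events are likely to be missed. It does not explain why the plan gives the Monitor's rating precedence and then withholds the events on which that rating could add something.

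Three stronger readings are tempting, and the documents do not support them.

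- *That the fate of an event the Monitor rejects is wholly undefined.* Safety Analysis read with the endpoint implies that it leaves the related-event summary. What is missing is a grade and a listing rule.
- *That unattributed harm would be invisible.* The number of deaths (Safety Analysis) and discontinuations with reasons (Subject Disposition) are reported with no stated relatedness condition. Safety Analysis also names vital signs, examination findings and ECGs, although Section 9 schedules no vital signs or examination, so their yield is uncertain.
- *That a new kind of device effect could not be recognised.* The Monitor's own UADE review does pass through the investigator's attribution. But the UADE definition does not rest on the investigator's opinion, the sponsor is separately responsible for ongoing safety evaluation, and a sponsor clinical specialist must attend each procedure.

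**Conclusion.** The point holds in a limited form. As written, the Monitor's governing rating can confirm or lower the investigator's attribution but has no route to raise one, so the analysed related-event count is bounded above by the investigator's count. The scale also lacks a not-related grade, and Sections 6 and 10 differ on which events the Monitor rates for relatedness.

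A reader might infer that the safety result will be understated. The documents do not show that: they give no rate of missed attribution, and the size of any understatement cannot be estimated. For scale only, if all 20 subjects are in the safety set, one subject with a missed event changes the proportion by 1/20 = 5 percentage points. The endpoint is descriptive, no pass/fail rule uses it, and the efficacy analysis is untouched. The severity is minor and the change is a cheap improvement. The conclusion assumes that sites follow the adverse event definition literally; sites that record more than it requires would narrow the gap.

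**What to change.** - **Section 10, opening paragraph and Definitions:** record on the CRF every untoward event from Test System pad placement to the end of the study visit, regardless of attribution. Align the sentence on baseline conditions and the serious-event reporting paragraph.
- **Section 6, Medical Monitor:** have the existing Monitor rate relatedness and seriousness of all recorded events, which also reconciles this section with Section 10.
- **Section 10, relationship scale:** add a not-related grade.
- **Section 7, Safety Analysis:** keep the declared endpoint as the events the Monitor rates at least possibly related, list the remaining events separately, and tabulate the investigator's rating beside the Monitor's.

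The cost is protocol and CRF wording plus a little more recording and review for 20 subjects. The downside is that some background events of the electrophysiology procedure will appear in the listing. The study visit is a sufficient window; extending surveillance beyond it would raise a separate question about length of follow-up and is not needed here.

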### **Subject Disposition**

Subject disposition including the number of subjects enrolled and number of subjects completing the study will be tabulated. The percentage of subjects completing the study will be based on the total number enrolled. Protocol deviations will also be summarized. Subject discontinuations and the reasons for discontinuation will also be summarized.

## 8 TEST SYSTEM

[figure not shown]
The Test System consists of a production-equivalent ASSURE WCD Monitor that will deliver the ASSURE defibrillation waveform (APPENDIX A). The ASSURE WCD Monitor will be from controlled inventory that is designated for clinical evaluations only. The Monitor will be connected to an ASSURE Defibrillation Adapter Module (ADAM) that allows use of a commercially-available Physio-Control LIFEPAK15 Therapy cable, and a commercially-available Physio-Control LIFEPAK15 5-wire ECG cable for patient connections.

Commercially available Physio-Control QUIK-COMBO RTS standard adhesive defibrillation electrodes will be applied in anterior and posterior positions that correspond to the defibrillation pad locations in the ASSURE WCD Garment. Standard adhesive defibrillation electrodes are used to limit interference with the electrophysiology procedure that the subject is otherwise undergoing. Otherwise, ASSURE WCD electrodes would also require the ASSURE Garment to hold the defibrillation electrodes in place on the body which may compromise the sterile field. Defibrillation efficacy using the QUIK-COMBO RTS electrodes is expected to be representative of defibrillation efficacy using ASSURE WCD electrodes since both types of electrodes have been designed and tested to meet the defibrillator electrode requirements as specified in IEC 60601-2-4 for electrode AC small signal impedance, AC large signal impedance and active area.

[figure not shown]
ECG signals will be monitored using 5 lead locations. Figure 1 shows an example of the Test System and EP monitoring setup to be used for the study, including the ASSURE WCD Monitor, the ADAM, and the EP monitor and backup rescue defibrillator. Figure 2 provides specific detail regarding the Test System defibrillation pad and ECG electrode placement.

Delivery of the ASSURE defibrillation waveform will be initiated by setting the ASSURE WCD Monitor to Manual Shock Mode. The Kestra Clinical Specialist will initiate the shock delivery on Investigator/Sub-Investigator command using the ASSURE Tablet that communicates with the ASSURE WCD Monitor via a Bluetooth connection (the Test System shock decision algorithm will not be used).

Figure 1: Example Test System and Monitoring Setup

**Figure 2: Test System Defibrillation Pad and ECG Electrode Placement**

### **Safety and Device Accountability**

Risks of this study have been identified through systematic hazard analysis, and the Sponsor has documented risk mitigation in a controlled Safety Risk Management Report.

Each ASSURE WCD Monitor and each ADAM will be assigned a unique serial number that is included on the labeling. Labeling also includes “For Investigational Use Only”. The Sponsor will maintain tracking records for all system components.

All Test System components will be accounted for by Kestra Clinical staff.

### **Reuse of System Components**

Adhesive ECG and defibrillation electrodes will be disposed of after use. Cables and Test System components will be cleaned between uses.

## 9 STUDY PROCEDURES

### Informed Consent and Enrollment

Cardiac patients will be screened for eligibility by the clinical site staff members in advance of the procedure date. Eligible patients will be provided the informed consent form and allowed enough time to review the consent, and to have any questions they may have adequately addressed. Only patients who provide written informed consent to participate can be enrolled as study subjects. Subjects will be considered enrolled after they have provided Informed Consent and when the Test System is connected to the defibrillation electrodes in step 5 of the Electrophysiology procedure below.

### Assessments

#### Demographic Data

Demographic data, including age, height, weight, gender, race, and ethnicity will be collected on the CRF.

#### Medical History

Medical history including information specified in the following list will be recorded on the CRF for each subject:

1. Disease process (ex., CAD, Dilated Cardiomyopathy, Hypertrophic Cardiomyopathy, Long QT/Brugada/CPVT)
2. Co-morbidities (ex., Diabetes, Renal disease, Hypertension, Hyperlipidemia, COPD)
3. Prior cardiac surgery (ex., PCI, CABG, other)
4. NYHA Class
5. The most recent left ventricular ejection fraction (%) measured by echocardiography, nuclear imaging (including MRI), or left ventricular angiography
6. History of Atrial arrhythmia
7. Prior Stroke/TIA
8. Baseline medications including any antiarrhythmic agents
9. Cardiac Implanted Electronic Device (i.e., pacemaker, ICD, CRT, ILR)
10. Shock therapy history from implantable or external devices

### **Clinical Laboratory Tests**

Pregnancy testing will be performed by urine HCG for women of child bearing potential prior to enrollment.

### **Supply, Packaging, Labeling, and Storage**

The Test System components will be provided by the Sponsor, including disposable defibrillation and ECG electrodes.

If Test System components are stored temporarily onsite, they must be stored at ambient room temperature in a securely locked cabinet or enclosure. Neither the Investigators nor any designees may provide devices to any individual not participating in this protocol.

### **Electrophysiology (EP) Procedure**

[figure not shown]
The following procedure will be performed during a single study visit corresponding to the EP procedure. A Kestra Clinical Specialist must be present.

1. (Investigator or qualified designee) Explain the purpose and conduct of the study visits to the subject, answer the subject's questions, and obtain written informed consent. Provide the subject with a copy of the informed consent. Consent can be completed in advance of the procedure date, or on the day of the Study Visit.
2. (Investigator) Review inclusion/exclusion criteria prior to any procedural activities
3. (Investigator or qualified designee) Assign Subject ID number
4. (Investigator or qualified designee) Record demographic data and protocol-specified medical history on case report form
5. (Investigator or qualified designee in consult with Kestra Clinical Specialist)  
Position two sets of disposable adhesive defibrillation pads on the patient's torso:
  - Locate one set provided by the Sponsor in the left anterior and left-subscapular posterior positions to be connected to the Test System (see Figure 2). This configuration will be used to deliver the experimental therapeutic defibrillation shock(s).
  - Locate the other set of defibrillation pads (not provided by the Sponsor for the backup rescue defibrillator) on the subject's torso according to physician preference but separated from the Test System defibrillation

pads to prevent arching or current shunt, and at least one inch away from a CIED if applicable.

- (Kestra Clinical Specialist) Obtain anterior and posterior photographs of the torso (not including subject's head/face) to document electrode placement.
- 6. (Kestra Clinical Specialist) Create a new patient in the ASSURE WCD Monitor, enter the subject ID number, and configure the ASSURE WCD Monitor to **manual** shock mode. (**Manual** shock mode allows the Study Shocks to be delivered on command by the physician)
- 7. (Investigator or Sub-Investigator) Induce a single sustained episode of rapid VT or VF  $\geq$  150 bpm via the CIED or an electrophysiology catheter.
  - If this protocol is performed as part of an ICD replacement procedure, the test procedure must be performed prior to surgical opening of the CIED pocket.
  - If using a CIED for induction, ventricular therapy (i.e., ATP and Shocks) must be programmed OFF or temporarily suspended while therapy from the Test System is delivered.
  - If the arrhythmia is less than 150 bpm, convert the patient's arrhythmia using the backup rescue defibrillator and/or standard of care procedures.
  - Repeated induction attempts may be performed to induce the ventricular rhythm. The investigator may stop induction attempts at any point if in their judgement it is no longer in the best interest of the patient.
  - Conversion is defined as the presence of a non-shockable rhythm (rhythms other than VT or VF) after shock delivery
- 8. (Kestra Clinical Specialist under the direction of the Investigator or Sub-Investigator) If the Arrhythmia is estimated to be greater than 150 bpm, deliver a 170J shock from the Test System.
- 9. (Kestra Clinical Specialist under the direction of the Investigator or Sub-Investigator) Deliver a second shock at 170J from the Test System if the first shock is unsuccessful.
- 10. (Investigator or Sub-Investigator) If both attempts to convert using the Test System are unsuccessful, convert the patient's arrhythmia using the backup rescue defibrillator, implantable defibrillator and/or standard of care procedures.

Time to the first shock from the Test System will be approximately 6 seconds. Total time to an external rescue shock, if needed, is estimated to be approximately 20 seconds.

